1.1 Background Information

Traumatic brain injury (TBI) is a leading cause of acquired disability in childhood, impacting long-term health and functioning. Hospitalizations and rehabilitation visits leave families with worries, guilt, and questions regarding longer-term issues. The impact of pediatric TBI on caregivers and families is clearly documented, with numerous studies showing poorer psychological functioning, greater stress, and more family problems among caregivers of children with TBI relative to caregivers of non-injured children (e.g., Aitken et al., 2009; Hawley et al., 2003; Rashid et al., 2014). Mounting evidence has supported the critical role of parent/family functioning and parent-child interactions in child recovery following TBI (Yeates et al., 1997; Taylor et al., 2001, Gerring & Wade, 2012), and recent investigations have continued to underscore the role of the family and home environment in the child's recovery.

Risk factors for poorer recovery include nonmodifiable factors such as greater severity of injury (Catroppa et al., 2008; Rassovsky et al., 2015), younger age at injury (Catroppa et al., 2008; Keenan et al., 2019), and lower household income (Cohen-Zimerman et al., 2019). However, there is a growing body of research documenting the critical role of caregiver and family functioning on child recovery following pediatric TBI (e.g., Ryan et al., 2016). Poor caregiver psychological functioning and family dysfunction have been found to exacerbate child behavior problems following injury (e.g., Raj et al., 2014a; Taylor et al., 2001). This association is particularly notable given that parents of children with TBI report more family problems, higher rates of depression and anxiety, and greater levels of stress than parents of non-injured children (e.g., Aitken et al., 2009; Hawley et al., 2003; Rashid et al., 2014). The influence of caregiver functioning is apparent in the initial months post injury, with poorer caregiver psychological health predicting more adolescent externalizing behavior problems, and more positive parent-adolescent communication predicting fewer behavior problems (Raj et al., 2014a).

To our knowledge, there are no interventions specifically targeting caregiver needs and well-being, and/or positive parenting in the acute phase following injury. Indeed, there is a general lack of interventions for families impacted by pediatric TBI (Brown et al., 2013). A number of existing interventions focus on chronic needs, and not on functioning in the immediate weeks after injury (McLaughlin et al., 2013, Wade et al., 2017). Parents of infants and toddlers may be especially unlikely to receive support; Keenan and colleagues (2019) found that more than 25% of parents of young children with TBI reported developmental concerns, yet only 5% of these children received early childhood intervention services.

Numerous factors can hamper intervention efforts with parents impacted by pediatric TBI. Parents already burdened with increased child needs may have not have time, resources, or inclination to seek supports for themselves (e.g., Roscigno & Swanson, 2011). Both traditional barriers to help seeking, such as perceived stigma (Corrigan, 2004), and logistical challenges such as living in rural areas or lack of transportation and financial resources (Syed et al., 2013) render traditional in-office psychological services difficult to access.

1.2 Rationale

The early recovery period constitutes a critical window to set families on a positive road-to-recovery by supporting parental self-care, positive parent-child interactions, and awareness of potential longer-term concerns. The latter would facilitate parental recognition of behavioral and psychosocial needs that might otherwise go unmet.

Recognizing that (1) caregivers of children who have sustained TBI are at risk of worsening psychological health and that (2) caregiver functioning and parenting behaviors have a direct impact on child recovery and outcomes; intervening and supporting caregivers in the acute phase following injury may set children and families on a positive path to recovery. Intervening at the acute phase may reduce the cascading effects of parental burden/distress and concomitant negative parent-child interactions on child recovery and functioning over time.

Because families of children with TBI and other chronic health conditions may have difficulty accessing services due to transportation and cost issues, particularly lower income families (Syed et al., 2013), the R2R-TBI program is designed to be accessed via any web-enabled device (e.g., smartphone, computer, tablet) with any form of internet connection. We will also offer the intervention (via tablet) to parents while they wait for their child to complete outpatient therapies (e.g., speech, physical, and occupational therapy). Delivery of web-based behavioral health interventions may reduce barriers to help-seeking and promote evidence-based interventions that are both accessible and efficient (e.g., Linardon et al., 2019; Luxton et al., 2011). The PEW Research Center (2019) indicates that about 92% of US adults ages 30-49 years and 96% of adults ages 18-29 years own a smartphone. Importantly, the common practice of seeking health information online (PEW Research, 2015) is correlated with changes in medical decision making, suggesting that online information seeking affects subsequent health-related decisions (Chen et al., 2018). Among 151 caregivers of children with TBI, 71% rated a self-guided online treatment format as convenient (versus only 18% who rated face-to-face treatment as convenient), providing further support for the acceptability of this approach (Wade et al., 2019).

2. Objectives and Purpose

The overarching aims of this project are to: (1) refine and enhance the R2R-TBI intervention, and (2) examine the efficacy of the R2R-TBI intervention in a randomized control trial.

Findings from our pilot usability trial were largely positive and are described in Raj et al., (2021). The R2R-TBI program targets caregiver psychological functioning, parenting behaviors, and family functioning in the first three months following pediatric TBI. Research shows that the impact of parent functioning and behaviors on child outcomes are apparent in the initial months following injury (e.g., Raj et al., 2014a), and intervening during this acute phase may serve a protective function to children and families. This project is unique as it shifts the emphasis on recovery and neuroprotection that is typically delivered exclusively to the child, to the caregiver/family. Moreover, intervening in the acute phase post-TBI may provide a new opportunity for preventative

behavioral health care and set families on a positive path to recovery.

3. Study Design

3.1 Overview

This study has two main goals: 1) to refine and enhance the R2R-TBI intervention; and 2) to examine the efficacy of the R2R-TBI intervention in a randomized control trial. To achieve the second goal, we will employ a between-groups randomized treatment design with repeated measures at baseline, one-month post-randomization, and at a six-month follow-up. The two conditions will be: a) usual medical care plus access to internet resources regarding pediatric brain injury (Internet Resources Comparison group, IRC), and b) usual medical care plus the R2R-TBI intervention (Road-to-Recovery group, R2R-TBI).

3.2 Infrastructure

Participants will be recruited from Cincinnati Children's Hospital Medical Center (CCHMC) and Nationwide Children's Hospital (NCH). CCHMC and NCH are fully accredited by the Association for the Accreditation of Human Research Protection Programs (AAHRPP), which promotes the highest quality research. To earn accreditation, organizations must provide tangible evidence – through policies, procedures, and practices – of their commitment to scientifically and ethically sound research and to continuous improvement. Potential participants will also be recruited through sharing of study information and study flyer at other hospitals and through organizations and associations serving children/families impacted by pediatric TBI.

3.3 Study Measures

Participants will complete the following self-report measures at baseline, one-month post-baseline, and six-month follow-up. The measures described below were chosen based on the following criteria: 1) brevity (to minimize respondent burden), 2) high levels of reliability and evidence of validity with this population, 3) sensitivity to the effects of TBI, and 4) sensitivity to the effects of intervention. All data will be collected online via REDCap.

Family demographics: Parents will complete a demographic survey that includes items related to annual family income, child and parent race/ethnicity, relationship to child, and services child is receiving.

Parent mental health functioning: The Patient-Reported Outcomes Measurement Information System (PROMIS) Anxiety Measure 4a (4 items) will be used to assess parent anxiety. The Center for Epidemiological Studies Depression Scale (CES-D; 10-items), will be used to measure parent depression. The CESD-10 is the short form of the original 20 item CES-D (Radloff, 1977). The Primary Care PTSD Screen for DSM-5 (PC-PTSD-5) will be used to assess for parent post-traumatic stress symptoms. The measure consists of 5-items (Prins, et al., 2015).

Parent wellbeing: Parent resilience will be assessed using the Connor-Davidson

Resilience Scale (10 items, Connor and Davidson, 2003) and parent self compassion and self-care behaviors will be assessed using the Mindful Self-Care Scale – Brief (24 items, Cook-Cottone, C. P. (2015)

Perceived parenting efficacy. The Caregiver Self-Efficacy Scale (CSES) is a 25 item self-report scale that measures parenting confidence and efficacy. Parents rate how comfortable they are in aspects of parenting, including their ability to control their child's behavior, praise their child, and say no to their child. Scores on the measure range from 25 to 100, with higher scores indicating greater perceived parenting efficacy. The CSES is a reliable and valid measure and has been shown to be sensitive to the effects of online, family-centered interventions for TBI (Wade et al., 2014).

Family functioning. Family functioning will be assessed using the 12 item Global Functioning Scale of the McMaster Family Assessment Device (FAD-GF, Epstein et al., 1983), a self-report measure of family functioning with established reliability and validity (Miller et al., 1985). Primary caregivers will rate their level of agreement (i.e., strongly agree, agree, disagree, strongly disagree) to statements reflecting their family's functioning. Scores on the FAD-GF range from 1 to 4 with higher scores indicating poorer family functioning. The FAD-GF is recognized by the Pediatric Common Data Elements (CDE) workgroup as a core measure of family functioning following TBI (McCauley et al., 2012).

Child/adolescent socioemotional functioning. Caregivers will complete the Pediatric Quality of Life Inventory (PedsQL – Short Form, for ages 2-18 years; Varni et al., 1999) or the Pediatric Quality of Life Infant Scales (for ages 1-24 months; Varni et al., 2011). The PedsQL is a reliable, valid, and widely used measure of child/adolescent quality of life and socioemotional functioning (Varni et al., 1999, 2011), with established validity and reliability in pediatric TBI samples (McCarthy et al., 2005). The measure provides a total scale score as well as two summary scores - physical health and psychosocial health. The psychosocial health summary score will be used as an outcome measure and the physical health summary score will be used to describe the sample. Scale scores are reported as mean scores for each scale, with higher scores indicating better functioning.

Burden of injury. The Family Burden of Injury Interview (FBII, Burgess et al., 1999) will be used to assess injury-related stress in the domains of child functioning and behavior, spousal relationship, and relationship with other members of the family in the acute phase following injury. The FBII is a reliable and valid assessment measure of injury-related burden for families affected by TBI (Burgess et al., 1999).

Feasibility and satisfaction. Ease of use of the program will be assessed by several measures of feasibility including usage analytics (i.e., trace data that captures time spent using the intervention, number of modules completed, time spent in each section/page of the intervention, keyboard input, etc.), as well as the System Usability Scale (SUS; Brooke, 1996). The SUS is an industry-standard scale consisting of 10 items with five Likert-scale response categories (*strongly agree* to *strongly disagree*). The SUS is easy to administer, widely used, and produces reliable and valid results (Bangor et al., 2008; Lewis, 2018). Parents will also complete an intervention satisfaction survey that has been adapted from prior web-based intervention studies (e.g., Kurowski et al., 2018;

Wade et al., 2012). The satisfaction survey captures both satisfaction with the content as well as with the web-delivery of the intervention. Caregivers will also provide qualitative feedback and suggestions via telephone and in-person interviews.

3.4 Eligibility Criteria

3.4.1 Study Subjects

3.4.1.1 Participant Inclusion Criteria

Caregivers will be eligible if they are over 18 years of age, and if their child meets all of the following criteria:

- Ages 3 months to 18 years at time of discharge from hospital
- Sustained a complicated mild to severe TBI as defined by a Glasgow Coma Scale (GCS) of 13-15 with imagining abnormalities or GCS 3-12 with or without imaging abnormalities
- Admitted overnight to the hospital
- 0-3 months post-discharge

3.4.1.2 Participant Exclusion Criteria

The caregiver will be excluded from participation if any of the following occur:

- Child did not survive the injury
- Child's head trauma was self-inflicted
- Child does not reside with parent/caregiver for study duration
- English is not primary language spoken in the home

3.5 Recruitment Procedures

Up to 200 participants will be enrolled in this RCT. Potential participants will be identified and recruited from the CCHMC and NCH Trauma Registry, inpatient units, and outpatient clinics such as rehabilitation clinics. Potential participants will also be recruited through sharing of study information and study flyer at other hospitals and through organizations and associations serving children/families impacted by pediatric TBI.

Recruitment at CCHMC and NCH

Parents/caregivers who are eligible to participate will receive the study brochure or flyer while they are at the hospital, when their child is discharged from the hospital and/or at follow-up visits or clinics. Eligible parents/caregivers may also receive the study brochure or flyer via mail and or email (see recruitment email). The study brochure and flyer includes a QR code to a website that has the information sheet for the study. Research personnel will connect with families at the hospital (e.g., at follow-up clinics or discharge) or via phone (see phone /in-person recruitment script). Parents will be provided information about the study during this contact and will have the opportunity to review the information sheet/consent form and ask questions. Study staff will document this consent process on a form that will be included in the study binder.

Recruitment through sharing of study information and flyer

Potential participants may also reach out to the study staff and request to be screened for the study. Study staff at CCHMC will screen potential participants for eligibility and families who meet criteria will be provided information about the study during this contact and will have the opportunity to review the information sheet/consent form and ask questions (see Road-to-recovery telephone script for potential participants who self refer). Study staff will document this consent process on a form that will be included in the study binder

For all

If the parent or individual is not interested, they will be thanked for their time and no further contact about the study will be made. If interest in the study is expressed, the parent will be sent a link to the study REDCap site. Parents will also be given the option to meet with study staff via videocall to orient the parent to the REDCap and/or study site and provide technical support. The study REDCap site opens with the study information sheet that provides contact details for study personnel. Participants who choose to participate will indicate consent by clicking a button at the bottom of the REDCap information sheet that reads, “YES, I acknowledge that I have viewed the information sheet and am voluntarily choosing to participate in this study.” Participants who click “YES” will then begin the baseline questionnaires. Participants who choose not to participate will click the “NO, I acknowledge that I have viewed the information sheet and I do not wish to participate in this study,” and they will receive a notification thanking them for their time and they will not be able to access the questionnaires.

After baseline measures have been completed, the predetermined randomization sequence will be used to randomize caregivers into one of the two conditions (R2R-TBI vs. IRC). Stratified randomization will be used to achieve balance in child’s age (< 5 years; ≥ 5 years) and injury severity. The randomization sequence will be based on a design with blocks of four or six chosen randomly within the sequence with equal probability. A pseudorandom number generator in R will be used, and the randomization sequence will be maintained by the statistician. Randomly varying block size reduces the chance that research staff will guess the next group assignment, minimizing unconscious bias. Block randomization with randomly mixed block sizes will then be performed with equal probabilities of assigning a participant to one of the two intervention groups.

4. Study Procedures

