4.1.3.2 Internet Resources Condition (IRC)

Caregivers in the web-based resources condition will be provided with a link and password to a website that provides links to a range of resources on pediatric TBI including local, state, and national brain-injury associations. These resources will also be provided to families in the R2R-TBI intervention. Essentially, families in the IRC condition will have access to the same links to resources without the specific intervention content/modules. This will enable us to equate the groups with regard to access to information and resources available on the internet. Parents in this group will also have access to technical support as well as the opportunity to contact the researchers with any questions/concerns.

Participants in both conditions will continue to receive usual care.

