We anticipate that the R2R-TBI intervention will be effective in both ameliorating problems evident at baseline and in preventing emergence of additional problems in family and child functioning at one and six-months post-baseline. To test this hypothesis, we will examine group differences in family functioning (FAD-GF, Epstein, Baldwin, & Bishop, 1983), family burden of injury (FBI, Burgess et al., 1999) and child socioemotional functioning (PedSQL Psychosocial Summary Score, Varni et al., 1999) at one and six-months post-baseline.

Hypothesis 3: We hypothesize that treatment effects will be moderated by household income and level of caregiver distress at baseline.

We expect families with greater social disadvantage (lower income, more stress) will benefit most from the R2R-TBI intervention. This hypothesis is consistent with previous research findings (e.g., Antonini et al., 2014; Raj et al., 2014b; Wade et al., 2012, 2015).

Variable distributions will be examined before carrying out inferential statistical procedures, and transformations will be made in cases where distributions are skewed or fail to meet the assumptions of normality. Non-parametric procedures will be employed in cases where transformations would be inappropriate or where analysis of frequencies is justified. Preliminary work will also involve computation of reliabilities and creation of derived variables that summarize performance on measures that are highly inter-correlated. To evaluate potential attrition bias, caregivers who drop out (i.e., those who access < 3 modules and/or who do not complete baseline or follow-up measures) will be compared to those who remain in follow-up on background characteristics as well as on outcomes measured prior to dropout. Factors related to dropout will be included as covariates in the analysis.

Analytic plan for hypotheses 1 and 2. The primary analysis will consist of a linear mixed-effect models used to examine changes in caregiver, family, and child functioning among participants in the R2R-TBI intervention and IRC groups from baseline to 6-months post-baseline. In addition, the one-month data will be included in a mixed model repeated measures analysis. This model allows for flexible modeling of the pattern of change in outcomes over time and uses all the data for a given participant, even if that participant is not seen at all assessments, allowing us to retain participants with missing assessments.

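### Section 5.1 leaves transformations, derived scores and dropout covariates to judgement after the data are seen, with no step that withholds arm, and its dropout rule itself reveals arm

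*Combined protocol and SAP*

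**What the plan says.** Section 5.1 (Statistical and Analytical Plans) leaves four decisions to be made from the data:

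- Scale: "transformations will be made in cases where distributions are skewed or fail to meet the assumptions of normality".
- Method: "Non-parametric procedures will be employed in cases where transformations would be inappropriate or where analysis of frequencies is justified".
- Composites: preliminary work includes "creation of derived variables that summarize performance on measures that are highly inter-correlated".
- Covariates: dropouts are compared with those who remain, and "Factors related to dropout will be included as covariates in the analysis". Dropouts are defined as "those who access < 3 modules and/or who do not complete baseline or follow-up measures".

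Section 5.1 does place the look at distributions ahead of inferential testing. It also bootstraps the backward elimination, but only for Hypothesis 3.

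On who knows arm, Section 3.5 states that "the randomization sequence will be maintained by the statistician". Its stated protection concerns enrolment: "Randomly varying block size reduces the chance that research staff will guess the next group assignment, minimizing unconscious bias". Section 4.1.3.2 says that the control arm receives the same resource links "without the specific intervention content/modules".

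**The concern.** Each of the four decisions changes the test of the arm difference, and each rests on a judgement that two competent analysts could make differently. If arm is visible at that point, the choice can drift towards the more favourable version without any intent. A reader of the results could not tell whether an outcome was transformed or merged because of its distribution or because of its result.

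This matters more here than in many trials. Section 3.3 makes the outcomes caregiver self-report. The two arms use visibly different websites (Sections 4.1.3.1 and 4.1.3.2), and no masking of caregivers is described. Analysis is therefore one of the few stages where masking is still practical. Hypothesis 1 also lists five caregiver outcomes without naming a single primary, so the open choices recur for each one.

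**Working it through.** **1. What is fixed and what is open.** The stated triggers are skew or non-normality, unsuitability of a transformation, high inter-correlation, and relation to dropout. None comes with a cut-off, a list of candidates or a decision date.

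**2. Is arm withheld?** The documents mention no masked analyst, coded arm, blinded data review or lock of these choices before arm is linked. The varying block size protects the next assignment and does nothing after enrolment. The Hypothesis 3 bootstrap does not reach Hypotheses 1 and 2.

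**3. The dropout rule.** Its two criteria are joined by and/or, so fewer than 3 modules is enough alone. An IRC caregiver has no modules, and 0 < 3, so read literally every control caregiver is a dropout. Comparing dropouts with those who remain then becomes partly a comparison of arms. If the module criterion is meant for R2R-TBI only, dropout is defined differently in the two arms. Either way the step uses data that identify arm, and hiding the arm label alone would not mask it.

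**4. Size, as an illustration.** There is no plan figure to reproduce: alpha, power, effect size, SD and expected dropout are not stated, and Section 3.5 gives only a ceiling of 200 participants.

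Assumed inputs:
- no treatment effect; two-sided 5%; 80 per arm; 4,000 simulated trials
- right-skewed outcome, gamma with shape 1.5; correlation with baseline 0.6
- three scales (raw, log, rank), each with or without three covariates (correlation 0.2 each): 3 × 2 = 6 options

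Model for each option: outcome = b0 + b1·arm + b2·baseline (+ covariates), with p the two-sided test of b1 = 0. *Fixed* rejects if p for one preset option is below 0.05. *Best of six* rejects if min(p1,…,p6) < 0.05. Six independent tests would give 1 − 0.95^6 = 26.5%. These six share the same data, so the rate is much lower.

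| Strategy, one outcome | False-positive rate |
|---|---|
| Fixed | 4.7%; 5.1% with separately written code |
| Best of six, either direction | 10.7%; 10.5% with separately written code |
| Best of six, in favour of R2R-TBI only | 5.1 to 5.2%, against 2.5% nominal |
| Raw or log scale by pooled skewness, arm not used | 5.1% |

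Ratios: 10.7/4.7 = 2.3, 10.5/5.1 = 2.1 and 5.1/2.5 = 2.0. Monte Carlo standard error: √(0.05 × 0.95/4000) = 0.3 points near 5%, and √(0.107 × 0.893/4000) = 0.5 points near 11%.

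**5. How far the answer depends on behaviour and on the menu.**
- If the scale follows a skewness threshold, even one computed separately in each arm, the rate is 5.9 to 6.0% at 80 per arm and 5.6 to 5.8% at 100 per arm, against 5.4% fixed. The thresholds were assumed.
- A wider menu (four scales, six covariate sets, N = 200, a different skewed outcome model) gives 5.4% fixed and 10.1% for the best scale and covariate set. Adding two derived scores gives 15.5% (13.5 to 17.4% as the assumed outcome-correlation parameter goes from 0.8 to 0.4).
- In that wider design, choosing scale and covariate without arm gives 5.1% at N = 200 and 5.4% at N = 160. The choice of derived score was not simulated with arm withheld.

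**The case against.** **The list-holder.** Keeping the sequence with a statistician rather than with recruiting staff supports allocation concealment. The documents never say that this person runs the analysis or makes the Section 5.1 choices. This stands in full: holding the list is not the fault. The point needs only the absence of any step that withholds arm from whoever decides.

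**The triggers.** The plan's triggers are properties of the data and not arm differences, and distributions are examined before testing. Fitting six models and keeping the smallest p-value would depart from the plan. This largely stands: following a skewness rule keeps error near nominal even when computed by arm. But Section 5.1 states no rule, so nobody could verify later that one was followed, and putting the look first does not mask it.

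**Pre-specification.** If thresholds and candidate lists were fixed in advance, masking would add little. That is true, and a dated plan with those rules would be an acceptable alternative. The masked route has the advantage of keeping the data-driven flexibility that the plan evidently wants.

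**A stronger inference.** A reader might conclude that the statistician will analyse with arm in view and select favourable versions. The documents do not support that; they are silent on who decides and what that person sees.

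**Conclusion.** The gap is real and worth closing, as an inexpensive improvement. Four discretionary choices bear on the Hypothesis 1 and 2 analyses without thresholds and without an arm-blind step, and the covariate step as written identifies arm.

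The consequence is a possibility whose size cannot be derived from the documents. Always keeping the best of six options roughly doubles the per-outcome false-positive rate, to about 10 to 11% two-sided, or about 5% in favour of R2R-TBI. This rests on the assumed alpha, sample size, skew, correlations and menu. It is a worst case for those six options only. A reader might take it as the error rate of this trial or as a ceiling, and it is neither: behaviour that follows the stated triggers sits near 5 to 6%, and a wider menu with derived scores exceeds 11%. No figure for at least one of five outcomes is given, because that would mix in multiplicity, which is a separate matter.

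**What to change.** In Section 5.1:

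1. Define dropout, in both arms, by missing follow-up assessments. Baseline need not enter, since Section 4.1.2 requires complete baseline forms before randomisation. Report module use separately, as engagement within R2R-TBI.
2. State that all choices on transformation, non-parametric analysis, derived variables and covariates are made on pooled data with the arm code and module-use data removed.
3. State that these choices are signed and dated before the arm code is merged, and that any later change is reported as post hoc.

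Item 1 is needed for item 2 to work: with module-use data removed, the current dropout rule could not be applied.

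In Section 3.5: keep the sequence in a restricted file apart from the analysis file, or in REDCap's randomisation function if that is available. The protocol mentions REDCap for consent and data collection only.

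Cost: a few sentences and one masked export. Someone other than the person making the choices must prepare that export, and checks that need arm, such as dropout by arm, wait until after the merge. No participant procedure changes.
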